A true positive fraction (TPF) is defined as the probability of MP-erMRI tests show disease re-classified results when participants truly have upgraded disease according to 12 core TRUS re-biopsies. A false positive fraction (FPF) is defined as the probably of MP-erMRI tests show re-classified disease results when no upgrade disease was observed on 12 core TRUS re-biopsies. A TPF (sensitivity) of 90% and FPF (1-specificity) of 6% would be considered promising, whereas a TPF of ≤70% and a FPF of ≥20% are unacceptable. Sample size is calculated using the formula with asymptotic variances as proposed by Pepe [71], followed by a set of 5000 simulation to assess that the power is adequate. Simulation was done using STATA scrsize package (http://labs.fhcrc.org/pepe/dabs/software.html). Results showed that with 120 participants (25% have upgrade

re-biopsy vs. biopsy prior to enrollment), 81% power can be achieved (1-sided alpha 0.1). This ensures that there is at least 80% chance of drawing a positive conclusion if the MP-MRI is 94% specific and 90% sensitive.

11.4 Primary Analysis:

The observed TPF and FPF will be summarized as percentages with 90% CI. Joint CIs for TPF and FPF will also be examined. A positive conclusion is drawn if the lower limit of TPF is above the minimally acceptable level of 70% and the upper limit of FPF is below the minimally acceptable level of 20%. Table below gives 80% confidence intervals for the true but unknown TPF and FPF, given possible observed participants with reclassified disease by MRI among 30 true reclassified and 90 non-reclassified cases (by re-biopsy). Table below is an example of 80% CI given different scenarios observed reclassified participants number.

Disease Upgra	ade by Re-bi	lopsy (n=30)	No Upgrade by Re-biopsy (N=90)		
Observed	Observed	80% CI	Observed	Observed	80% CI
reclassified	TPF		Reclassified	FPR	
N by MRI			N by MRI		
27	90%	(79%, 96%)	5	6%	(3%, 10%)
25	83%	(71%, 92%)	10	11%	(7%, 17%)
23	77%	(64%, 87%)	15	17%	(12%, 23%)
21	70%	(57%, 81%)	18	20%	(15%, 26%)

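### The primary success rule in section 11.4 has no confidence level or method: 90% intervals are announced, 80% intervals are tabulated, and the choice can reverse the conclusion

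*Combined protocol and SAP*

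**What the plan says.** Section 11.4 (Primary Analysis) opens with the level for the primary summary: "The observed TPF and FPF will be summarized as percentages with 90% CI". The next sentence adds "Joint CIs for TPF and FPF will also be examined", with no level, construction or role in the decision.

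The success rule follows: "A positive conclusion is drawn if the lower limit of TPF is above the minimally acceptable level of 70" per cent, together with an upper limit of FPF below 20%. It names no level, no sidedness and no interval method.

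The text then moves to a different level: "Table below gives 80% confidence intervals for the true but unknown TPF and FPF", and again "Table below is an example of 80% CI given different scenarios observed reclassified participants number". Both interval columns of the table are headed 80%. Its row for 25/30 gives 71% to 92%.

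Section 11.3 reports 81% power with 120 participants at a one-sided alpha of 0.1. It does not say whether that alpha applies to each criterion or jointly to both. On method it says "Sample size is calculated using the formula with asymptotic variances", followed by 5000 simulations, and it concludes "This ensures that there is at least 80% chance of drawing a positive conclusion" if the MRI is 94% specific and 90% sensitive.

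**The concern.** Three readings of the rule are open.

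1. Two-sided 90% limits decide, because that is the interval announced at the start of 11.4.
2. The 90% interval is descriptive and two-sided 80% limits decide, because these correspond to a one-sided alpha of 0.1 per criterion and are what the table shows.
3. The announced 90% interval means one-sided 90% limits, which are numerically the same as two-sided 80% limits.

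This rule alone determines whether MP-erMRI is declared adequate, and both criteria must be met. Two analysts working correctly from the same page could report opposite primary conclusions. If the level is not fixed in advance, it could be settled after the counts are known.

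**Working it through.** **Inputs.** From 11.2 and 11.3: 120 men, 25% upgraded, so 30 upgraded and 90 not; design alternative TPF 90% and FPF 6%; unacceptable values TPF 70% and FPF 20%. From 11.4: thresholds 70% and 20%; levels 90% (text) and 80% (table).

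**Step 1: the method behind the printed table.** Exact (Clopper-Pearson) limits for x events in n at two-sided level 1 − a are the a/2 quantile of Beta(x, n − x + 1) and the 1 − a/2 quantile of Beta(x + 1, n − x). At 80% they reproduce all eight printed intervals after rounding. For example, 27/30 gives 79.1% to 96.3% (printed 79%, 96%) and 10/90 gives 7.0% to 16.6% (printed 7%, 17%). Other methods do not fit: for 27/30 the lower limit is 81% (Wilson), 80% (logit), 83% (Wald) or 81% (Jeffreys). The table is therefore exact, although the text does not say so.

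**Step 2: where the verdict changes (exact limits).**

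| Result | Limit that decides | 80% | 90% | Verdict |
|---|---|---|---|---|
| 24/30 | lower | 67.5% | 64.3% | fails at both |
| 25/30 | lower | 71.3% | 68.1% | **changes** |
| 26/30 | lower | 75.1% | 72.0% | passes at both |
| 11/90 | upper | 17.9% | 19.4% | passes at both |
| 12/90 | upper | 19.1% | 20.7% | **changes** |
| 13/90 | upper | 20.4% | 22.0% | fails at both |

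The 80% rule is therefore at least 25/30 and at most 12/90. The 90% rule is at least 26/30 and at most 11/90.

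**Step 3: power.** Power = P(X ≥ k) × P(Y ≤ m), with X ~ Bin(30, 0.90) and Y ~ Bin(90, 0.06).

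- 80% rule: 0.9268 × 0.9972 = 0.9242.
- 90% rule: 0.8245 × 0.9925 = 0.8183, close to the stated 81%.

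If the number upgraded is Bin(120, 0.25) and the cut-offs are re-derived for each split, power is 90.2% and 80.2%. The claim of at least 80% holds either way.

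**Step 4: how often the rules disagree at the design alternative.** Every success under the 90% rule is also a success under the 80% rule, so disagreement = 0.9242 − 0.8183 = 0.106. Of this, P(X = 25) × P(Y ≤ 12) = 0.1020 and P(X ≥ 26) × P(Y = 12) = 0.0039. With a random split the figure is 90.2% − 80.2% = 10.0%.

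**Step 5: chance of meeting each criterion at its unacceptable value.**

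- TPF 70%: P(X ≥ 25) = 7.7% (80% rule); P(X ≥ 26) = 3.0% (90% rule).
- FPF 20%: P(Y ≤ 12) = 6.9% (80% rule); P(Y ≤ 11) = 3.8% (90% rule).

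**Step 6: does the stated alpha identify the level?** Read per criterion, one-sided 0.1 corresponds to two-sided 80% limits. Read as joint and split equally, each criterion gets 1 − √0.9 = 0.0513, which corresponds to 89.7% limits and the same cut-offs as 90% (26/30 and 11/90). Section 11.3 supports either reading.

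**Step 7: does the stated power identify the level?** Section 11.3 cites an asymptotic formula without giving its scale. On an assumed logit scale, power per criterion = Φ(|logit p1 − logit p0| × √(n p1(1 − p1)) − z). At one-sided 0.10 each this gives 0.8255 × 0.9636 = 79.5%; at 0.05 each, 0.7168 × 0.9238 = 66.2%. On that assumption, 81% lies nearer the 80%-limit reading. The exact rule in step 3 points the other way.

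**The case against.** The best counter-reading is that the question has an answer. The opening sentence of 11.4 sets 90%, the rule comes two sentences later, and the natural antecedent of its limits is that interval. The 80% table comes after the rule and is offered as an example. The power supports this: with the 30/90 split, 90% limits give 81.8% by the exact, Wilson or logit method, while at 80% no method tried gives less than 92.4%. The logit formula in step 7 rests on an assumed scale. Untransformed versions at one-sided 0.10 give 95.5% or 99.1%, and the 81% may come from the simulations instead.

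The consequence is also bounded. With exact limits the rules differ by one count per criterion and agree in 89.4% of trials at the design alternative. Both keep each boundary error below 10%.

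Much of this stands. The 90% sentence and the power figure do favour 90%, the logit result is only indicative, and there is no inflation of error. It remains an inference, though. The rule does not cite the 90% interval, the 80% level appears twice in the text and in both column heads, and one-sided 0.1 per criterion matches the table.

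The method matters too. Wilson and logit limits change the verdict at 25/30 and 12/90, and also at 13/90. With Jeffreys limits 25/30 passes at both levels and 12/90 changes. With Wald limits both counts pass at both levels.

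**Conclusion.** The concern holds and needs to be fixed before analysis. The primary decision is not uniquely defined, and under either reading something on the page does not fit. If 90% governs, the only worked table shows 25/30 clearing 70% when it would fail. If 80% governs, the announced interval is not the deciding one, and the exact rule has about 90–92% power, not 81%.

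The effect is confined to results at the margin, mainly 25/30, which accounts for 10.2 of the 10.6 percentage points of disagreement. The figures assume exact limits, TPF 90% and FPF 6%, independence between the two groups of men, and the planned split (or a binomial split with 25% upgraded). The conclusion does not depend on the logit calculation.

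**What to change.** In 11.4, name one confidence level and the exact (Clopper-Pearson) method for both limits in the success rule, and say that the joint intervals are descriptive if they play no part in it. In 11.3, say whether alpha 0.1 is per criterion or joint. The sponsor then chooses one of two consistent versions.

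- **(a) Two-sided 90% exact limits.** Replace the table: 27/30, 76–97%; 26/30, 72–95%; 25/30, 68–93%; 5/90, 2–11%; 10/90, 6–18%; 11/90, 7–19%; 12/90, 8–21%. Power stays at about 80–82%.
- **(b) Two-sided 80% exact limits, one-sided 0.1 per criterion.** Keep the table, label the 90% interval as descriptive only, and restate the power of the exact rule as about 90–92%.

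In either case, state that the limits are computed from the observed numbers of upgraded and non-upgraded men, since 30 and 90 are only expected values. With 25 upgraded of 120, the 80% rule needs at least 21/25 and at most 13/95, and the 90% rule at least 22/25 and at most 12/95. With 35 upgraded, the cut-offs are 29/35 and 11/85 (80%) against 30/35 and 10/85 (90%).

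The cost is wording in 11.3 and 11.4 plus one replaced table (a) or one restated power figure (b). No change to participants or data collection is needed.

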11.5 Secondary Objectives

Determine the frequency of MP-erMRIs which appear to reclassify men with low risk disease considering AS.

Determine the effect of MP-erMRI and repeated 12 core TRUS biopsy on patient-reported health states.

Correlate the pathology findings from the targeted biopsy with the MP-erMRI findings for those men who fall into the reclassified category.

11.6 Secondary Analysis

Secondary analysis will be summarized descriptively. Number and percentage of participants with reclassified disease by MP-erMRI will be summarized as numbers and percentages with 90% CI. Participants will be asked to complete self-reported health state questionnaires at enrollment and following the final on-protocol biopsy. A score will be given for each questionnaire answered by participants. The scores for the questionnaires will be summarized as median and inter-quartile ranges. Descriptive statistics will be utilized to correlate the targeted biopsy findings (disease extent in mm and Gleason score) with the findings from the MP-erMRI.

Appendix B

SERVICES SATISFACTION SCALE - FOR CANCER CARE (SSS-Ca)

The following questions are about your satisfaction with the cancer care you received

Please indicate the answer that best describes your feeling about each aspect of the services you have received. We are interested in your overall experience during the last year with care or therapy that you have received related to your cancer therapy or its side effects. By "practitioner" we mean the one or more doctors, clinicians, etc., who have worked with you in your cancer-related care.

What is your overall feeling about the . . .

	Completely satisfied	Very satisfied	Somewhat satisfied	Mixed	Somewhat unsatisfied	Very unsatisfied	Completely unsatisfied
Effect of health care services in helping you deal with your cancer and maintain your well being?	1	2	3	4	5	6	7
Effect of cancer treatment in preventing cancer progression or recurrence?	1	2	3	4	5	6	7
How well your confidentiality and rights as an individual have been protected?	1	2	3	4	5	6	7
Quality of cancer care you have received?	1	2	3	4	5	6	7
In an overall general sense, how satisfied are you with the cancer treatment you have received?	1	2	3	4	5	6	7

Name:	
Signature:	Date:

Appendix C:

•	cer Index Composite for Clinica	•	PIC-CP)					
	y, bowel, sexual and vitality/hormonal healt r the following questions by che		propriate chec	khov Allau	octions are ab	out your bo	alth	
	AST FOUR WEEKS. Select one an			KDOX. All qu	estions are au	out your ne	aicii	
1. Overall, how much	of a problem has your urina	ry function	been for you	ı?				
1 □ No problem 2	□ Very small problem 3 □ Sm	nall problem	4 □ Modera	ite problem	5 □ Big pro	blem		
2. Which of the follow	ving best describes your urin	ary control	?					
0 Total Control 1	. □ Occasional dribbling 2 □ F	requent drib	bling 4 □ No	o urinary cor	ntrol	-		
3. How many pads or	adult diapers per day have	you been us	sing for urina	ry leakage	?			
0 □ None 1 □ One	pad per day 2 □ Two pads pe	erday 4⊡	Three or more	pads per da	у	-	_	
4. How big a problem	, if any, has urinary dripping	or leakage	been for you	1?				
0 □ No problem 1	□ Very small problem 2 □ Sm	all problem	3 □ Modera	te problem	4 □ Big prob	lem _		
	Clinicians: ADD the answers from qu	estions 2-4 to c	alculate the Urina	ry Incontinenc	e Symptom Score	(out of 12):		
5. How big a problem following been for	, if any, has each of the you?	No Problem	Very small problem	Small problem	Moderate problem	Big problem		
a. Pain or burning with	h urination	0 🗆	10	2 🗆	3 🗆	4 🗆	_	
b. Weak urine stream,	incomplete bladder emptying	0 🗆	1 🗆	2 🗆	3 🗆	4 🗆	_	
c. Need to urinate fre	quently	0 🗆	1 🗆	2 🗆	3 🗆	4 🗆	_	
Clinicians	: ADD the answers from questions 5a-5	ic to calculate t	he Urinary Irritati	on/Obstruction	Symptom Score	(out of 12):		
6. How big a problem	, if any, has each of the	No	Very small	Small	Moderate	Big		
following been for	•	Problem	problem	problem	problem	problem		
_	ncy of bowel movements	0 🗆	10	2 🗆	3 🗆	4 🗆		
b. Increased frequenc	y of your bowel movements	0 🗆	10	2 🗆	3 🗆	4 🗆	_	
c. Overall problems w	c. Overall problems with your bowel habits 0 1 2 3 4 4 4 4 4 4 4 4 4 4 4 4 4 4 4 4 4 4							
	Clinicians: ADD the answ	vers from quest	ions 6a-6c to calc	ulate the Bow	I Symptom Score	(out of 12):		
7. How would you ra	te your ability to reach orgas							
0 □ Very good 1□	Good 2 □ Fair 3 □ Poor	4 □ Very po	or to none			_	_	
8. How would you de	scribe the usual quality of yo	our erection	ıs?					
0 □ Firm enough for 1 □ Firm enough for masturbation 2 □ Not firm enough for 4 □ None at all intercourse and foreplay only any sexual activity								
9. Overall, how much	of a problem has your sexua	al function	or lack of sex	ual functio	n been for v	ou?		
9. Overall, how much of a problem has your sexual function or lack of sexual function been for you? □ □ No problem □□ Very small problem □□ Small problem □□ Moderate problem □□ Big problem □□ □□								
	Clinicians: ADD the an	swers from que	stions 7-9 to calc	ulate the Sexua	I Symptom Score	(out of 12):		
10. How big a proble	m, if any, has each of the	No	Very small	Small	Moderate	Big	_	
following been for	_	Problem	problem	problem	problem	problem	_	
a. Hot flashes or breas	st tenderness/enlargement	0 🗆	1 🗆	2 🗆	3 🗆	4 🗆	_	
b. Feeling depressed		0 🗆	1 🗆	2 🗆	3 🗆	4 🗆	_	
c. Lack of energy		0 🗆	1 🗆	2 🗆	3 🗆	4 🗆	_	
	Clinicians: ADD the answers from ques	tions 10a-10c t	o calculate the Vi	tality/Hormon	I Symptom Score	(out of 12):		
N	Sanatura			Dote				

AUA Symptom Index	Name:
-------------------	-------

Please answer the following questions by checking the appropriate check box. All questions are about your health and symptoms in the **LAST FOUR WEEKS**. Select one answer for each question.

	not at	less than	less than 1/2	about 1/2	more than	almost
	all	1 in 5	the time	the time	1/2 the time	always
Over the past month or so, how often have you had a sensation of not emptying your bladder completely after you finished urinating?	0	1	2	3	4	5
During the past month or so, how often have you had to urinate again less than 2 hours after you finished urinating?	0	1	2	3	4	5
During the past month or so, how often have you found you stopped and started again several times when you urinated?	0	1	2	3	4	5
During the past month or so, how often have you found it difficult to postpone urination?	0	1	2	3	4	5
During the past month or so, how often have you had a weak urinary stream?	0	1	2	3	4	5
During the past month or so, how often have you had to push or strain to begin urination?	0	1	2	3	4	5
Over the past month, how many times per night did you most typically get up to urinate from the time you went to bed at night until the time you got up in the morning?	0 times	1 time	2 times	3 times	4 times	5 or more times

	Delighted	Pleased	Mostly satisfied	mixed	mostly dissatisfied	Unhappy	Terrible
How would you feel if you had to live with your urinary condition the way it is now, no better, no worse, for the rest of your life?	0	1	2	3	4	5	6

Signature:	Date:

Appendix E:

Adult Comorbidity Evaluation-27

Identify the important medical comorbidities and grade severity using the index. Overall Comorbidity Score is defined according to the highest ranked single silment, except in the case where two or more Grade 2 allments occur in different organ systems. In this situation, the overall comorbidity score should be designated Grade 3.

		norbidity score should be designated Grade 3.	
Cogent comorbid	Grade 3	Grade 2	Grade 1
ailment	Severe Decompensation	Moderate Decompensation	Mild Decompensation
Cardiovascular Syste			
Myocardial Infarct	☐ MI ≤ 6 months	□ MI > 6 months ago	☐ MI by ECG only, age undetermined
Angina / Coronary Artery Disease	□ Unstable angina	□ Chronic exertional angina □ Recent (≤ 6 months) Coronary Artery Bypass Graft (CABG) or Percutaneous Transluminal Coronary Angioplasty (PTCA) □ Recent (≤ 6 months) coronary stent	□ ECG or stress test evidence or catheterization evidence of coronary disease without symptoms □ Angina pectoris not requiring hospitalization □ CABG or PTCA (>6 mos.) □ Coronary stent (>6 mos.)
Congestive Heart	☐ Hospitalized for CHF within past 6	☐ Hospitalized for CHF > 6 months prior	☐ CHF with dyspnea which has
Failure (CHF)	months □ Ejection fraction < 20%	☐ CHF with dyspnea which limits activities	responded to treatment □ Exertional dyspnea □ Paroxysmal Nocturnal Dyspnea (PND)
Arrhythmias	□ Ventricular arrhythmia ≤ 6 months	 □ Ventricular arrhythmia > 6 months □ Chronic atrial fibrillation or flutter □ Pacemaker 	☐ Sick Sinus Syndrome ☐ Supraventricular tachycardia
Hypertension Venous Disease	□ DBP≥130 mm Hg □ Severe malignant papilledema or other eye changes □ Encephalopathy □ Recent PE (≤ 6 mos.) □ Use of venous filter for PE's	□ DBP 115-129 mm Hg □ DBP 90-114 mm Hg while taking antihypertensive medications □ Secondary cardiovascular symptoms: vertigo, epistaxis, headaches □ DVT controlled with Coumadin or headrin	□ DBP 90-114 mm Hg while not taking antihypertensive medications □ DBP <90 mm Hg while taking antihypertensive medications □ Hypertension, not otherwise specified □ Old DVT no longer treated with Coumadin or Heparin
D : 1 - 14 - : 1		□ Old PE > 6 months	-
Peripheral Arterial Disease	 □ Bypass or amputation for gangrene or arterial insufficiency < 6 months ago □ Untreated thoracic or abdominal aneurysm (≥6 cm) 	 □ Bypass or amputation for gangrene or arterial insufficiency > 6 months ago □ Chronic insufficiency 	 □ Intermittent claudication □ Untreated thoracic or abdominal anewrysm (< 6 cm) □ s/p abdominal or thoracic aortic anewrysm repair
Respiratory System			
	□ Marked pulmonary insufficiency □ Restrictive Lung Disease or COPD with dyspnea at rest despite treatment □ Chronic supplemental O₂ □ CO₂ retention (pCO₂ > 50 torr) □ Baseline pO₂ < 50 torr □ FEV1 (< 50%)	 □ Restrictive Lung Disease or COPD (chronic bronchitis, emphysema, or asthma) with dyspnea which limits activities □ FEV1 (51%-65%) 	☐ Restrictive Lung Disease or COPD (chronic bronchitis, emphysema, or asthma) with dyspnea which has responded to treatment ☐ FEV1 (66%-80%)
Gastrointestinal Syst	em		
Hepatic	□ Portal hypertension and/or esophageal bleeding ≤ 6 mos. (Encephalopathy, Ascites, Jaundice with Total Bilirubin > 2)	☐ Chronic hepatitis, cirrhosis, portal hypertension with moderate symptoms "compensated hepatic failure"	□ Chronic hepatitis or cirrhosis without portal hypertension □ Acute hepatitis without cirrhosis □ Chronic liver disease manifested on biopsy or persistently elevated bilirubin (>3 mg/dl)
Stomach / Intestine	□ Recent ulcers(≤ 6 months ago) requiring blood transfusion	□ Ulcers requiring surgery or transfusion > 6 months ago	□ Diagnosis of ulcers treated with meds □ Chronic malabsorption syndrome □ Inflammatory bowel disease (IBD) on meds or h/o with complications and/or surgery
Pancreas	 □ Acute or chronic pancreatitis with major complications (phlegmon, abscess, or pseudocyst) 	 □ Uncomplicated acute pancreatitis □ Chronic pancreatitis with minor complications (malabsorption, impaired glucose tolerance, or GI bleeding) 	☐ Chronic pancreatitis w/o complications

Cogent comorbid	Grade 3	Grade 2	Grade 1
ailment	Severe Decompensation	Moderate Decompensation	Mild Decompensation
Renal System	•	•	·
End-stage renal disease	□ Creatinine > 3 mg% with multi-organ	□ Chronic Renal Insufficiency with	□ Chronic Renal Insufficiency with
	failure, shock, or sepsis	creatinine >3 mg%	creatinine 2-3 mg%.
	☐ Acute dialysis	□ Chronic dialysis	
Endocrine System	(Code the comorbid ailments with the (*) in		rgan systems if applicable)
Diabetes Mellitus	☐ Hospitalization ≤ 6 months for DKA	□ IDDM without complications	□ AODM controlled by oral agents only
	☐ Diabetes causing end-organ failure	□ Poorly controlled AODM with	
	 □ retinopathy □ neuropathy 	oral agents	
	□ nephropathy*		
	□ coronary disease*		
	□ peripheral arterial disease*		
Neurological System			
Stroke	☐ Acute stroke with significant neurologic	☐ Old stroke with neurologic residual	☐ Stroke with no residual
	deficit	· ·	□ Past or recent TIA
Dementia	□ Severe dementia requiring full support for	☐ Moderate dementia (not completely	☐ Mild dementia (can take care of self)
	activities of daily living	self-sufficient, needs supervising)	,
Paralysis	☐ Paraplegia or hemiplegia requiring full	□ Paraplegia or hemiplegia requiring	□ Paraplegia or hemiplegia, ambulatory
_	support for activities of daily living	wheelchair, able to do some self care	and providing most of self care
Neuromuscular	☐ MS, Parkinson's, Myasthenia Gravis, or	□ MS, Parkinson's, Myasthenia	☐ MS, Parkinson's, Myasthenia Gravis,
	other chronic neuromuscular disorder and	Gravis, or other chronic	or other chronic neuromuscular
	requiring full support for activities of daily	neuromuscular disorder, but able to	disorder, but ambulatory and
	living	do some self care	providing most of self care
Psychiatric			
	□ Recent suicidal attempt	☐ Depression or bipolar disorder	☐ Depression or bipolar disorder
	☐ Active schizophrenia	uncontrolled	controlled w/ medication
		□ Schizophrenia controlled w/ meds	
Rheumatologic	(Incl. Rheumatoid Arthritis, Systemic Lupus		
	□ Connective Tissue Disorder with secondary end-organ failure (renal,	□ Connective Tissue Disorder on steroids or immunosuppressant	☐ Connective Tissue Disorder on NSAIDS or no treatment
	cardiac, CNS)	medications	NSALDS of no dealment
Immunalarical System	(AIDS should not be considered a comorbidi		lin's Lamphama
AIDS	☐ Fulminant AIDS w/KS, MAI, PCP (AIDS		☐ Asymptomatic HIV+ patient.
	defining illness)	CD4+< 200/µL	☐ HIV w/o h/o AIDS defining illness.
			CD4+> 200/μL
Malignancy	(Excluding Cutaneous Basal Cell Ca., Cutan	eous SCCA. Carcinoma in-situ. and In	traenithelial Neonlasm)
Solid Tumor including	☐ Uncontrolled cancer	☐ Any controlled solid tumor without	☐ Any controlled solid tumor without
melanoma	□ Newly diagnosed but not yet treated	documented metastases, but	documented metastases, but initially
	□ Metastatic solid tumor	initially diagnosed and treated	diagnosed and treated > 5 years ago
		within the last 5 years	
Leukemia and	□ Relapse	□ 1* remission or new dx <1yr	☐ H/o leukemia or myeloma with last
Myeloma	□ Disease out of control	□ Chronic suppressive therapy	Rx > 1 yr prior
Lymphoma	□ Relapse	☐ 1st remission or new dx <1yr	☐ H/o lymphoma w/ last Rx >1 yr prior
		☐ Chronic suppressive therapy	
Substance Abuse	(Must be accompanied by social, behavioral		
Alcohol	□ Delirium tremens	☐ Active alcohol abuse with social,	☐ H/o alcohol abuse but not presently
		behavioral, or medical complications	drinking
TE-5 D	TA A THE A TOTAL A TOT		The shape of the s
Illicit Drugs	☐ Acute Withdrawal Syndrome	☐ Active substance abuse with social,	☐ H/o substance abuse but not presently
		behavioral, or medical complications	using
Body Weight		Compactions	
Obesity Obesity		☐ Morbid (i.e., BMI ≥ 38)	
Oversity		□ Matout (i.e., DMI = 30)	

Rev November 2003 Washington University School of Medicine Clinical Outcomes Research Office

SERVICES SATISFACTION SCALE – FOR CANCER CARE (SSS-Ca)

The following questions are about your satisfaction with the cancer care you received

Please indicate the answer that best describes your feeling about each aspect of the services you have received. We are interested in your *overall experience during the last year* with care or therapy that you have received related to your cancer therapy or its side effects. By "practitioner" we mean the one or more doctors, clinicians, etc., who have worked with you in your cancer- related care.

What is your overall feeling about the . . .

	Completely satisfied	Very satisfied	Somewhat satisfied	Mixed	Somewhat unsatisfied	Very unsatisfied	Completely unsatisfied
Effect of health care services in helping you deal with your cancer and maintain your well being?	1	2	3	4	5	6	7
Effect of cancer treatment in preventing cancer progression or recurrence?	1	2	3	4	5	6	7
How well your confidentiality and rights as an individual have been protected?	1	2	3	4	5	6	7
Quality of cancer care you have received?	1	2	3	4	5	6	7
In an overall general sense, how satisfied are you with the cancer treatment you have received?	1	2	3	4	5	6	7

Name:		
Signaturo:	Dato:	

AUA	Symptom	Index
-----	----------------	-------

Name:

Please answer the following questions by checking the appropriate check box. All questions are about your health and symptoms in the **LAST FOUR WEEKS**. Select one answer for each question.

	not at all	less than 1 in 5	less than 1/2 the time	about 1/2 the time	more than 1/2 the time	almost always
Over the past month or so, how often have you had a sensation of not emptying your bladder completely after you finished urinating?	0	1	2	3	4	5
During the past month or so, how often have you had to urinate again less than 2 hours after you finished urinating?	0	1	2	3	4	5
During the past month or so, how often have you found you stopped and started again several times when you urinated?	0	1	2	3	4	5
During the past month or so, how often have you found it difficult to postpone urination?	0	1	2	3	4	5
During the past month or so, how often have you had a weak urinary stream?	0	1	2	3	4	5
During the past month or so, how often have you had to push or strain to begin urination?	0	1	2	3	4	5
Over the past month, how many times per night did you most typically get up to urinate from the time you went to bed at night until the time you got up in the morning?	0 times	1 time	2 times	3 times	4 times	5 or more times

	Delighted	Pleased	Mostly satisfied	mixed	mostly dissatisfied	Unhappy	Terrible
How would you feel if you had to live with your urinary condition the way it is now, no better, no worse, for the rest of your life?	0	1	2	3	4	5	6

Signature: _____ Date: ____

MISHEL UNCERTAINTY INDEX – COMMUNITY FORM FOR ACTIVE SURVEILLANCE (MUIS-AS)

The following questions are about your feelings about your cancer diagnosis:

Please indicate the answer that best describes your feeling about each aspect of the services you have received. We are interested in your overall experience during the **last year** with care or therapy that you have received related to your cancer therapy or its side effects

Please respond to the following questions, indicating the extent to which you feel the following emotions about your prostate cancer:

Feeling	Not at all	A little	A moderate amount	A lot	A great deal
Worried	0	1	2	2	-
worried	0	1	2	3	4
Fearful	0	1	2	3	4
Anxious	0	1	2	3	4
Confident	0	1	2	3	4
Hopeful	0	1	2	3	4
Eager	0	1	2	3	4
Angry	0	1	2	3	4
Sad	0	1	2	3	4
Disappointed	0	1	2	3	4
Guilty	0	1	2	3	4
Disgusted	0	1	2	3	4
Exhilarated	0	1	2	3	4
Pleased	0	1	2	3	4
Нарру	0	1	2	3	4
Relieved	0	1	2	3	4

Signature:	Date:

Expanded Prostate Cancer Index Composite for Clinical Practice (EPIC-CP)

A clinical tool to measure urinary, bowel, sexual and vitality/hormonal health

Patients: Please answer the following questions by checking the appropriate checkbox. All questions are about your health and symptoms in the LAST FOUR WEEKS. Select one answer for each question

1 □ No problem	2 □ Very small problem	3 □ Small p	roblem	4 □ Modera	te problem	5 □ Big pro	blem
Which of the foll	owing best describes yo	ur urinary	control	•			
0 □ Total Control	1 ☐ Occasional dribbling	2 □ Frequ	ent drib	oling 4 🗆 No	o urinary cor	itrol	
How many pads	or adult diapers per day	have you	been us	ing for urina	ry leakage?	•	
0 □ None 1 □ O	ne pad per day 2 🗆 Two	pads per day	4 □	Three or more	pads per da	у	
How big a proble	em, if any, has urinary di	ripping or l	eakage	been for you	?		
0 □ No problem	1 ☐ Very small problem	2 □ Small p	roblem	3 □ Moderat	te problem	4 □ Big prob	lem
	Clinicians: ADD the answers	from question	s 24 to ca	lculate the Urinar	y Incontinence	Symptom Score	(out of 12): _
How big a proble following been f	em, if any, has each of th for you?		No oblem	Very small problem	Small problem	Moderate problem	Big problem
. Pain or burning	with urination		0 🗆	1 🗆	2 🗆	3 □	4 □
. Weak urine strea	am/incomplete bladder em	ptying	0 🗆	1 🗆	2 🗆	3 □	4 □
Need to urinate	frequently		0 🗆	1 🗆	2 □	3 □	4 □
Clinicia	ans: ADD the answers from quest	ions 5a-5c to c	alculate tr	e Urinary Irritatio	n/Obstruction	Symptom Score (out of 12): _
How big a proble following been f	em, if any, has each of th for you?		No oblem	Very small problem	Small problem	Moderate problem	Big problem
. Rectal pain or urg	gency of bowel movements	5	0 🗆	1 🗆	2 🗆	3 □	4 □
. Increased freque	ncy of your bowel moveme	ents	0 🗆	1 □	2 □	3 □	4 □
Overall problems	with your bowel habits		0 🗆	1 🗆	2 □	3 □	4 □
How would vou	Clinicians: ADD rate your ability to reach			ons 6a-6c to calcu	ılate the Bowel	Symptom Score	(out of 12): _
_	-	Poor 4 □	-				
	describe the usual qualit						•
☐ Firm enough for	1 □ Firm enough for n	nasturbation	2 [] Not firm eno	ugh for	4 □ None at	all
tercourse	and foreplay only		an	/ sexual activit	у		
Overall. how mu	ich of a problem has you	ır sexual fu	nction (or lack of sex	ual functio	n been for v	ou?
•	1 □ Very small problem					4 □ Big prob	
	Clinicians: AD	DD the answers	from que	stions 7-9 to calcu			(out of 12): _
	lem, if any, has each of		No	Very small	Small	Moderate	Big
following been f	•		oblem	problem	problem	problem	problem
	east tenderness/enlargemedd		0 🗆	1 🗆	2 🗆	3 □	4 🗆
. reening depresse			0 □	1 🗆	2 🗆	3 🗆	4 □
Lack of energy				1 □	2 □	3 □	4 □

Clinicians: ADD the answers from questions 10a-10c to calculate the Vitality/Hormonal Symptom Score (out of 12): _

Name:	Signature:	Date:
